**Long term follow up (at 18 months)**

Neurodevelopmental follow up is a part of the routine follow up of infants with Neonatal Encephalopathy. Bayley II examination at 18 months of age is used to compare the results from this study with our large local patient database and previous randomised controlled trials (CoolCap, Gluckman 2005; TOBY, Azzopardi 2009) [10, 11] where Bayley II was also used: we were a main recruiting centre for these trials.

Disability will be defined as any of:

Bayley II mental developmental scale score (MDI) less than 70.

Bayley II motor development scale score (PDI) less than 70. MDI and PDI will also be calculated as developmental quotients (DQ), as this allows a larger range of score for those functioning at a low level [35].

Bilateral cortical visual impairments.

Hearing loss needing amplification > 40 DB.

**Additionally:**

We will do both short-term (14 days) and long-term (18 months survival) follow-up. In cooled babies we have shown that short-term predictors such as MRI at ~day 8 [2], time to normalisation of aEEG [1] and peak LDH before 72h [4] predict long-term outcome with a positive predictive value of 84%, 92% and 80% respectively. In this study we will be able to examine these predictors for cooled babies receiving xenon treatment. By defining these relationships one can calculate the sample size for a large trial using short-term outcome.

**7.6 Study Data**

All the patient study information will be coded by patient study number, anonymised and securely stored until the study is complete. Electronic data will be stored on a secure portion of a Hospital Trust computer. The Chief Investigator will ensure that all the patient identifying details have been removed prior to statistical analyses being undertaken.

The identification key linking study numbers to patient details will be kept by the CI ([name]) in a locked filing cabinet in a locked office in the Neonatal Neuroscience office of St. Michael's Hospital Bristol, which also has two separate secure swipe card entry systems.

Reference:	CH
Issue:	2
Revision:	3
Issue Date:	1 May 2013
Page	37 of 49

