**Secondary Objectives:**

We will monitor a number of variables before/during and after the period of xenon delivery. This group of physiological and biochemical parameters includes those recorded during our recently completed xenon+cooling feasibility/safety study in neonates and a few more are added .

They are:

Gas exchange: Transcutaneous oxygen saturation, end-tidal carbon dioxide concentration, blood gas data (from arterial sample), mechanical ventilation requirements (rate, peak inspiratory pressure, PEEP settings).

Haemodynamic: Systolic, mean and diastolic arterial pressure, heart rate.

Any problems during weaning and extubation, such as post-extubation stridor, use of steroids.

We have also looked at other variables in the infants cooled in our hospital (inborn or outborn) ca 30/year since 1/12/06. We chose the best matched controls (3:1) from this cooling database and compared them with the 14 infants in the recent Xenon + cooling human feasibility study (the precursor to this study),

We will also record:

- 1] Coagulopathy [INR >2, APTT> 50]
- 2] Inotrope requirement, cardiac Troponin T
- 3] Hepatic impairment, [raised Alanine aminotransferase > 40, Alkaline phosphatase > 100, peak Lactate dehydrogenase within 72h of age
- 4] Renal impairment, oliguria [urine output < 1 ml/kg/h after day 1 of life and raised creatinine > 100]
- 5] Infection [culture proven, need for antibiotics  $\geq$  5 days, raised CRP  $\sim$  within the first 24h and at 4 days of life of life]
- 6] Number of anticonvulsive drugs needed to treat seizures
- 7] Length of hospital stay
- 8] Time to full oral feed by bottle or breast
- 9] MRI assessment by T1 and T2 weighted images using the scoring system by Rutherford et al [2].
- 10] In some infants when the 3Tesla MRI scanner is available assessment of brain metabolites using magnetic resonance spectroscopy (MRS) where the ratio Lactate/N-acetyl aspartate has

Reference:	CH
Issue:	2
Revision:	3
Issue Date:	1 May 2013
Page	5 of 49

	been shown to be a good early biomarker for outcome [5].  Safety

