#### **Early predictors of outcome**

#### **For the main analysis we will use**

Time to recovery after birth of a normal aEEG [1]

MRI scan before 14 days of life [33, 2]

Peak LDH value within 72h of life [4, 34]

We will also collect data on:

Plasma glucose at birth (in cord blood)

Age in hours after birth when plasma lactate has fallen to 5mmol/L

Different inotropic drugs needed and the total duration in hours of any inotropic support

Number of anticonvulsants given

Amount and duration of sedation (e.g.morphine)

Age at full oral feeds (breast or bottle or tube)

Neonatal hearing screening result before 14 days of life

Clinical examination at birth, at 7 days of age and at discharge including weight and head circumference

Neurodevelopmental follow up is a part of the routine follow up of infants with HIE, Bayley examination at 18 months of age.

Disability will be defined as any of:

Bayley II mental developmental scale (MDI) score less than 70.

Bayley II motor development scale (PDI) score less than 70. MDI and PDI will also be calculated as DQ, developmental score as this allows a larger range of score for those functioning at a low level [35]. Bilateral cortical visual impairments Hearing loss needing amplification > 40 DB.

In addition any Adverse Events will be recorded and criteria have been devised for stopping the study early if necessary. This includes a Data Review Panel to review data when 4 xenon infants have undergone xenon treatment.

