## Clinical management

- 1) The neonates would be sedated, mechanically ventilated and cooled according to the protocol for cooling listed above, as this is standard treatment. In the case of retrieved babies, cooling is always started before transfer to Bristol (active or passive cooling). If not before, active cooling starts when the transport team arrives. Antibiotics, fluid management and sedative drugs used would be unmodified.
- 2) Neonates would be entered into the study according to the set criteria within a maximum of 5hrs of birth with respect to adding xenon to the existing underlying standard cooling regime which has started within 3 hrs (passive or active).

Reference:	CH
Issue:	2
Revision:	3
Issue Date:	1 May 2013
Page	18 of 49

*Specific clinical management of cooling group*

1. This group will be cooled according to the normal protocols of the hospital as this is standard treatment.

*Specific clinical management of xenon+cooling group*

After initial resuscitation and attainment of a stable state, and inclusion in the study, the tracheal tube would be replaced with a cuffed commercially available tracheal tube (Kimberley-Clark microcuff) of the same or 0.5mm smaller size as the existing one and the cuff inflated until leakage of gas around the cuff had ceased audibly and according to the ventilator monitor. This particular tube has a high volume, low pressure cuff and is specifically designed for long term use on the paediatric or neonatal intensive care unit. The cuff pressure will be monitored and recorded at the time of initial inflation, during xenon administration every 2 hours and just prior to final deflation. If there are any post extubation adverse events such as stridor, or extubation fails secondary to vocal cord, nerve or subglottic damage, these will be recorded. The experience from our recent neonatal feasibility/safety study was that of the 14 babies, one baby developed post-extubation stridor requiring steroids. \* See Appendix 4.

\*In a recent very large study of cuffed tracheal tubes for anaesthesia in infants and neonates, the use of a cuffed tube did not increase risk of post-extubation stridor. In 2246 children, post-extubation stridor was noted in 4.4% of those with a cuffed tracheal tube and 4.7% of those with uncuffed tubes, with a much lower tube exchange rate in the cuffed tube group. See Appendix 11.

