#### Long term follow up (at 18 months)

Reference:	CH
Issue:	2
Revision:	3
Issue Date:	1 May 2013
Page	24 of 49

Neurodevelopmental follow up is a part of the routine follow up of infants with Neonatal Encephalopathy. Bayley II examination at 18 months of age is used to compare the results from this study with our large local patient database and previous randomised controlled trials (CoolCap, Gluckman 2005; TOBY, Azzopardi 2009) [10, 11] where Bayley II was also used: we were a main recruiting centre for these trials.

Disability will be defined as any of:

Bayley II mental developmental scale score (MDI) less than 70.

Bayley II motor development scale score (PDI) less than 70. MDI and PDI will also be calculated as developmental quotients (DQ), as this allows a larger range of score for those functioning at a low level [35]. Bilateral cortical visual impairments.

Hearing loss needing amplification > 40 DB.

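### The treatment is visible at the bedside, yet the protocol does not require aEEG and MRI, two of its three main markers, to be scored without knowledge of allocation

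*Protocol*

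**What the plan says.** Section 2.1 (early predictors of outcome) lists the main-analysis markers: "Time to recovery after birth of a normal aEEG", an MRI scan within the first 14 days, and the peak LDH within 72 hours. The Protocol Summary (Secondary Objectives, item 9) describes "MRI assessment by T1 and T2 weighted images using the scoring system", so the MRI result is a score given by a reader. Sections 3.2 and 7.5.4 place the MRI findings and the timing of aEEG normalisation among short-term investigations made before discharge, as part of routine practice.

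The arms look different. In the xenon arm, "the tracheal tube would be replaced with a cuffed commercially available tracheal tube" (section 3.1, Clinical management), and xenon is given through a dedicated circuit between ventilator and infant (section 4.1). Controls are cooled under the usual hospital protocol. No sham is described.

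At 18 months, "Bayley II examination at 18 months of age is used to compare the results from this study with our large local patient database" (section 3.2).

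On data handling, section 7.6 says "All the patient study information will be coded by patient study number, anonymised and securely stored until the study is complete". It then says "The Chief Investigator will ensure that all the patient identifying details have been removed prior to statistical analyses being undertaken", and that "The identification key linking study numbers to patient details will be kept by the CI". It does not mention treatment allocation or the people who read traces and scans.

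**The concern.** When staff can see the treatment, the usual protection for a judged outcome is a reader who does not know the arm. The protocol asks for none. The hour at which an aEEG background counts as normal and the score given to an MRI both leave room for judgement, and knowledge of the arm can move that judgement in one direction without anyone intending it.

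The direction matters because section 2.0 hypothesises that the early predictors will lean towards xenon plus cooling. Section 9.1 says that differences between groups will be estimated, and sections 2.0 and 3.3 say that the markers will feed power calculations for a larger trial. A one-sided reading shift would enter those estimates and so the planning of the next trial. Masked reading also protects the investigators, whose group developed both the treatment and the delivery device.

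**Working it through.** The protocol gives no figure for this point, so the check sets its statements side by side.

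**1. Is allocation visible?** Yes. Tube exchange and xenon circuit are present in one arm only (sections 3.1 and 4.1), with usual cooling in the other and no sham.

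**2. Which outcomes depend on judgement?**

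| Outcome | Source of the value | When | Masked assessment required in the text at hand? |
|---|---|---|---|
| Time to normal aEEG (main) | Reader of the trace | Recorded continuously until after rewarming | No |
| MRI (main) | Reader, scoring system | Before 14 days, preferably days 7–12 | No |
| Peak LDH (main) | Laboratory | Within 72 h | Not needed |
| Bayley II (long term) | Examiner | 18 months | No |

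Two of the three main markers therefore depend on a reader, as does the long-term outcome.

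**3. Does any provision cover the readers?**
- Section 6.0 assigns a study number straight after enrolment.
- Section 13.6 keeps names off the case report forms.
- Section 13.5 requires a subject identifier on source documents, including MRI scans.
- Section 7.6 codes and anonymises the data.

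All four deal with identity. A coded record can still show the arm, and a named scan can be read by someone who does not know the arm. None of them answers the masking question.

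**4. Are the readings used to compare the arms?** Yes: sections 2.0, 3.3 and 9.1, as described above.

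**5. How far could masking succeed?** Xenon starts by 5 h of age at the latest and lasts 18 h, so it ends by 5 + 18 = 23 h of age.
- The MRI comes days later and would carry no trace of the circuit, so it can be masked well once annotations and notes are withheld.
- The aEEG recording includes the xenon period. The protocol describes xenon as sedative (section 3.1, Risks/benefits), so that part of the trace might be recognisable. Masking of the aEEG may be incomplete.
- Parents will know the arm and may mention it to the Bayley examiner.

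**The case against.** **The study is a descriptive pilot.** Section 9.1 makes recruitment feasibility the main purpose, puts second whether markers in the cooled-only group match historical controls, and disclaims power to test outcome. This stands as far as it goes: knowing the arm does not affect how many infants can be recruited early. It does not dispose of the point, because the same protocol estimates differences between arms and plans to use the markers in later power calculations.

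**Silence is not proof of unmasked reading.** This is fair. No reader is named and no order of scoring is given. Some pages and the appendices were not available, so the absence applies only to the text at hand. The protocol shows that unmasked reading is possible, not that it occurs, and a reader might go too far in concluding that the team which developed the device will score its own traces and scans. Masking of outcome readers is nevertheless a design matter that belongs in the protocol.

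**Masking is not free.** aEEG is read clinically for entry and for seizures, and MRI is routine care, so a masked score may need a second, research-only reading. This stands and is counted in the cost.

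A reader might also infer from section 7.6 that identifiers come off only after scoring, and that this rule creates the bias. The documents do not support that. The same section says that all study information is coded, with no time limit; study numbers exist from enrolment; and nothing fixes when scoring happens. Since removing identifiers is not masking, removing them earlier would not cure the problem.

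**Conclusion.** The point holds as a gap in the design. Two of the three main-analysis markers are reader-dependent in a visibly unmasked trial, and the text at hand does not require them to be scored without knowledge of allocation. The between-arm marker differences are open to assessment bias. The feasibility aim and peak LDH are not affected on this ground. The change is worth making because it is cheap; the gap does not invalidate the study.

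The size of any bias cannot be calculated from the protocol. A tempting comparison is that one reclassified MRI in an arm of 16 moves a proportion by 1/16 = 6.25 points, two by 12.5 and three by 18.75, set against the 66% − 51% = 15 points quoted for cooling in section 1.2. It should not be used. It needs a normal/abnormal MRI result, whereas the protocol specifies a score. The 15 points refer to death or disability, a different outcome. Two scans would in any case fall short of it. Nothing in the documents shows that any such shift takes place.

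The conclusion assumes that no masking provision sits in the pages not seen, and that the pre-discharge readings would otherwise serve as the study values.

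**What to change.** In sections 2.1 and 3.2, state that for the study analysis:
- aEEG recordings and MRI scans are exported under the study number, with dates and treatment annotations removed (age in hours is kept on the aEEG, since the marker is counted from birth);
- existing readers score them without access to allocation or clinical notes;
- the scores are locked before allocation is joined.

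Ask that the 18-month Bayley examiner not be told the arm where possible. State in the report that masking of the aEEG during xenon, and of the Bayley when parents know the arm, may be incomplete.

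The rule can also cover the 15 infants recruited by April 2013 (8 cooling, 7 xenon), provided that their recordings and scans are still held. Clinical reading for care continues unchanged.

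The cost is a few sentences of protocol text, file handling, and possibly a research read separate from the clinical one. No extra infants or patient procedures are needed.

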### 7.7 GP Notification

The General Practitioner will be informed via a letter of the participation of the infant in the study when the infant is discharged from hospital.

## 8.0 Assessment of Safety

### 8.1 Data Review Group.

An external Data monitoring Group will be set up and appropriately constituted with clearly defined terms of reference. Their role will be to independently review the safety of the study after every 4th xenon patient has been recruited i.e.

every 4 xenon babies and in the light of this make appropriate recommendations to the study team.

The group will meet when every 4 xenon-treated babies have been enrolled. The Data Monitoring Group will also meet in the event of a death, regardless of cause. This meeting will take place within ~14 days of the death and recruitment into the study will continue in the meantime. This meeting could be in person or take the form of a teleconference.

N.B. In our previous neonatal feasibility/safety study of xenon+cooling a partial external committee met at intervals of every other baby enrolled. One outcome of this study was that the xenon gas itself did not cause any significant physiological or biochemical changes or other problems and neither did the use of a breathing system functionally the same as the one to be used in this study. This explains our choice of a 4 enrolled xenon baby interval for the xenon+cooling group in this study.

### 8.3 Criteria for stopping the study (stopping rule) have been developed according to the following logic:

The underlying mortality is approximately 25% in this cohort of infants (without xenon). Usually care is redirected based on futility, i.e. the clinical condition and state of the brain is such that no meaningful life can be expected.

#### Reasons for stopping Xe delivery before the 18h timepoint:

Cardiovascular problems sometimes present as untreatable hypotension. In this situation the heart has also suffered hypoxia-ischaemia and sometimes we are unable to keep a perfusion pressure even with the use of maximum inotropic support.

Another problem would be if the neonate develops a very high oxygen fraction (up to 100%) in the breathing gas over time, >40% according to the study entry criteria. An example would be those who have aspirated meconium.

#### Stopping rule:

Mortality since cooling became standard of care at St Michaels hospital (inborn and outborn) fell from 34% to 25%. With this (25%) underlying mortality it is not unlikely, for example, that the two first infants might die ( $p=0.06$ ). If the study is allowed to continue and also the third infant in the xenon group dies, the probability that this is a random event is very small ( $p=0.016$ ) and recruitment should be stopped and the protocol reviewed.

From then on (n is the number of 'xenon' babies included in the study):

n deaths

- 3 3 of 3 stop
- 4 3 of 4 stop
- 5 4 of 5 stop
- 6 4 of 6 stop
- 7 4 of 7 stop
- 8 5 of 8 stop
- 9 5 of 9 stop
- 10 5 of 10 stop
- 11 5 of 11 stop
- 12 6 of 12 stop

If a few more than 12 infants were to be included in the xenon arm of this study the number of deaths used as the stopping number should be 40% of the total number.

This stopping rule is based on two considerations:

1. Probabilities given 25 % mortality without Xe
2. Stricter rule with more babies included

(See Appendix A6)

Reference:	CH
Issue:	2
Revision:	3
Issue Date:	1 May 2013
Page	40 of 49

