Patient Population	Newborn infants $\geq$ 36 weeks gestation which satisfy all St Michael's Hospital standard inclusion criteria for cooling (i.e. at risk of brain injury following poor condition at birth) and which additionally satisfy the inclusion criteria of this investigation for the administration of xenon by inhalation. Cooling should be started within 3h of age and xenon within 5. Use of a shorter treatment delay in these entry criteria will optimize the possibility of finding an effect if there is one.
Population Size	16 babies in each of 2 groups
Structure	Single centre prospective randomised clinical pilot study
Duration of Participation	Xenon administration period of 18 hours. Recruitment period up to 18 months from start of study. Short and long term monitoring until 18 months of age. Therefore total study duration 3 years.
Method of Assignment	Comparative study. Neonates meeting all entry criteria can be included.
Randomisation	Patients will be randomised between cooling (standard treatment) and xenon+cooling groups as this is a comparative study. Patients will be randomised on a 1:1 basis to receive either conventional cooling therapy or cooling plus xenon therapy.

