## 9.0 Data Analysis and Statistical Plan

### 9.1 Statistical Analysis

This is a randomised pilot study. Data presentation will include descriptive statistics only. These will be compared in the 2 treatment groups but also to recordings of the same variables in a similar group of 45 infants (recruited to cooling only from the same entry criteria) recently treated in our department (historical control data). Differences between the groups will be estimated

Sample size is 16 infants in each group. In accordance with the paper by Julius (Appendix 11), 12 is a large enough number to estimate the mean value of short term outcome variables for the group. The study does of course not have the power to test outcome. The main purpose of this randomised pilot study is to examine whether early recruitment is feasible, secondly whether the short term biological markers show the expected range of values in the cooled only group as compared to our historical controls. Our advisory statistician for this study is [name] who also advised all our experimental xenon work as well as the recent clinical feasibility study.

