### 9.2 Interim Analysis and Stopping Rules

See 8.0 – 8.3 above which describes interim analysis and stopping rules in detail.

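### Protocol 8.1 and 8.3 give opposite instructions on recruitment after a death that reaches a mortality limit, and no text at hand says which one governs

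*Protocol*

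**What the plan says.** Protocol 8.3, under the stopping rule, assumes 25% underlying mortality. It says that if the first three xenon infants all die, "recruitment should be stopped and the protocol reviewed". From there it lists the number of deaths that means stop: 3, 3, 4, 4, 4, 5, 5, 5, 5, 6 for n = 3 to 12, where n is the number of xenon "babies included in the study". Beyond 12 the number is 40% of the total, with no rounding stated. Section 9.1 now sets the arm at 16: "Sample size is 16 infants in each group".

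Protocol 8.1 schedules a review after every fourth xenon baby and also says: "The Data Monitoring Group will also meet in the event of a death, regardless of cause". It continues: "This meeting will take place within ~14 days of the death and recruitment into the study will continue in the meantime".

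Section 9.2 refers to 8.0 to 8.3 together as the text "which describes interim analysis and stopping rules in detail". Section 12.0 refers only to the stopping rule in section 8. Section 8.2 (listed in the contents) and Appendix A6 are not in the text at hand.

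**The concern.** A xenon-arm death that reaches a limit is covered by both instructions. Under 8.3 recruitment stops. Under 8.1 it goes on until a meeting that may be about two weeks away. Someone who follows 8.1 to the letter would keep enrolling, and giving xenon, after the trial's only numerical mortality boundary had been reached.

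There is a second, weaker consequence. Because n counts babies included, each xenon baby enrolled before the meeting raises n at once. Where the limit steps up at the next n, the deaths already counted may no longer reach it. The text at hand does not say whether the count at the death or at the meeting decides.

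**Working it through.** **The plan's own figures.** 0.25² = 0.0625 (printed 0.06) and 0.25³ = 0.0156 (printed 0.016). Both reproduce.

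**Only a death can reach a listed limit.** The listed limits never fall from n = 3 to 12, so including a living baby cannot bring the count up to a limit. Every stop on the list is therefore also a death under 8.1.

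**Where one more living baby takes the count back under.** The limit rises at n = 4→5, 7→8 and 11→12. So 3 of 4, 4 of 7 and 5 of 11 are stops, while 3 of 5, 4 of 8 and 5 of 12 are not. For n = 13 to 16, 40% is 5.2, 5.6, 6.0 and 6.4. Rounded up this gives 6, 6, 6, 7, which adds a step at 15→16.

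**Where the trial stands.** The Protocol Summary reports 7 xenon babies recruited by April 2013; this version is dated 1 May 2013. So n = 4 is past, and n = 7 is past or, if a death among the seven could still occur, pending. The values clearly ahead are n = 11 and n = 15.

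**Chance of reaching a limit.** Assume independent babies, 25% mortality, and each outcome known before the next baby. The chance that the limit r(n) is first reached at n is 0.25 × P(no limit so far and r(n) − 1 deaths after n − 1 babies).

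| n | 3 | 4 | 6 | 7 | 9 | 10 | 11 | 13 | 14 | 15 |
|---|---|---|---|---|---|---|---|---|---|---|
| chance | .0156 | .0352 | .0132 | .0264 | .0096 | .0192 | .0283 | .0091 | .0176 | .0252 |

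It is zero at n = 5, 8, 12 and 16.

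- No limit by n = 7: 1 − (.0156 + .0352 + .0132 + .0264) = 0.910.
- Given that, n = 8 to 12: (.0096 + .0192 + .0283)/0.910 = 6.3%.
- Given that, n = 8 to 16: (.0571 + .0091 + .0176 + .0252)/0.910 = 12.0%.
- n = 11 alone: .0283/0.910 = 3.1%. n = 15 alone: .0252/0.910 = 2.8%.

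**Chance of a further xenon baby within 14 days** (Poisson arrivals; all rates are assumptions).

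- Planned pace, 16 xenon babies over "Recruitment period up to 18 months from start of study" (the 18 months taken in full): 16/(18 × 30.44) × 14 = 0.409; 1 − e^(−0.409) = 34%.
- Ceiling, every one of the "infants cooled in our hospital (inborn or outborn) ca 30/year since 1/12/06" entered 1:1, so 15 xenon babies a year: 15/365.25 × 14 = 0.575; 1 − e^(−0.575) = 44%.
- Slower, 7 in 15 months to 12 in 18 months: 0.215 to 0.307, so 19% to 26%.

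**Chance that a reached limit lapses**, if recruitment continues, the added baby is alive, and the list is applied to the later count.

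- n = 11 only: 3.1% × 34 to 44% = 1.0 to 1.4%.
- n = 11 and 15: 5.9% × 34 to 44% = 2.0 to 2.6%.
- At the slower rates: from 3.1% × 19% = 0.6% to 5.9% × 26% = 1.5%.

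Lapses that need two or more added babies (for example from n = 10) are left out.

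**The case against.** The best answer is that 8.1 is a general default and 8.3 a specific exception. At 25% mortality several deaths are expected, so a default that a single death does not pause recruitment makes sense. An instruction to stop recruitment has force only if it overrides that default. Section 12.0 points to the stopping rule for discontinuation, and 8.3 itself allows for the study continuing after two deaths. This is a fair reading and may be what was meant. It does not settle the matter, because 8.1 is unqualified and neither 9.2 nor 12.0 sets an order.

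Section 8.2 and Appendix A6 are not shown and may say who applies the limit and on what count. That stands: their silence cannot be claimed as a gap. Unless they set an order, the two visible sentences still need aligning.

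A reader might infer that the protocol lets a reached limit be undone by further enrolment. The documents do not support that. It needs 8.1 to prevail and the list to be applied again to a larger n, and no text at hand directs the second step. The ordinary reading of a sequential boundary is that reaching it is the stop.

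A reader might also start from the first baby. That gives a 14.7% chance of reaching a limit by n = 12, with 61% of it at n = 4, 7 or 11. The arithmetic is right, but it describes a trial with no xenon babies yet, and this version was issued with seven already recruited.

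**Conclusion.** The conflict between 8.1 and 8.3 is real in the text at hand. It applies to every xenon-arm death that reaches a listed limit. It deserves correction because it concerns the only numerical mortality boundary and the correction is cheap.

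The size is modest. For the rest of the trial, a limit is reached with a chance of 6.3% at n = 8 to 12 and about 12% at n = 8 to 16. A limit that lapses during the wait has a chance of about 1 to 3%, or 0.6 to 1.5% at the slower recruitment rates. These figures assume 25% mortality, no limit reached by n = 7 (deaths so far are not reported), the 40% clause rounded up and, for the lapse, a later count being used. The contradiction itself depends on none of them. What tempers confidence is the unseen text and the available reading of 8.3 as the overriding rule.

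**What to change.** The sponsor, the advisory statistician and the review group should reconcile 8.1 and 8.3. Both sections should state the same action on recruitment between a limit-reaching death and the meeting. They should also state that the limit is judged on one defined count, at the death or at the meeting. Which course to adopt is for them to decide.

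In the same edit, print integer limits for n = 13 to 16, since the list ends at 12 and the arm is now 16. Rounding matters: 40% of 13 is 5.2, so rounding down or to the nearest whole number would give 5, below the 6 listed at n = 12. A surviving baby could then reach the limit.

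The cost is one or two sentences and four integers, with no extra babies or data. If the agreed text pauses recruitment, up to about 14 days are lost at a limit, or about 2 × 0.409 = 0.8 to 2 × 0.575 = 1.15 babies over both arms. If it continues recruitment, about 0.4 to 0.6 further xenon babies are expected to be enrolled after a limit has been reached.
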